### **7.4. Justification for the Study Design**

Pathway PV system, which is the first generation model of JETSTREAM™ Atherectomy System (Jetstream), received 510(K) approval in July 2008, and then, the current generation model (Jetstream) in April, 2013. Also, it received CE-Mark certification in September 2013. JETSTREAM™ Atherectomy System is now commercially available in the U.S., EU, Australia or other foreign areas and its' effectiveness and safety have been confirmed.

The Jetstream China trial is designed to evaluate the safety and effectiveness of JETSTREAM™ Atherectomy System (Jetstream) for treating symptomatic Chinese patients with occlusive atherosclerotic lesions in native SFA and/ or PPA, in whom sufficient revascularization cannot be expected from the PTA alone during endovascular treatment in the opinion of operating physician. The Jetstream China trial is a single arm clinical trial compared to the safety performance goal (PG). The PG was set based on published data of PTA/stenting outcomes in the recent clinical trial.

This trial requires at least one roll-in subject per site.

During the trial, dual antiplatelet therapy (DAPT) will be administered for 6 months post index procedure and aspirin use will be required indefinitely post index procedure. Ongoing dynamic data safety monitoring will be performed throughout the trial to minimize subject risk. All enrolled subjects receiving the Jetstream system treatment will be followed for 12 month post index procedure.

### **7.5. Treatment**

All enrolled subjects will receive treatment with the investigational Jetstream System. Pre-dilation of target lesion is prohibited prior to the treatment of Jetstream System. After target lesion is adequately treated by the Jetstream System, PTA and/or stenting with commercially-available device(s) are allowed for optimizing treatment.

The investigator selects the size of Jetstream Catheter according to the proximal and distal reference vessel diameters

**Handling Instructions of Study Devices**

**It is important for investigators to follow the corresponding DFU for Jetstream system treatment and for the study device product matrix.**

## **8. Subject Selection**

### ***8.1. Study Population and Eligibility***

Approximately 80 patients with symptomatic PAD of the femoropopliteal artery (Rutherford clinical category of 2 to 4) receiving percutaneous transluminal balloon angioplasty will be screened for enrollment of this study. Clinical and angiographic inclusion and exclusion criteria for the JETSTREAM China trial are included in Section 8.2 and Section 8.3 respectively. Prior to enrollment in the trial, a subject should meet all of the clinical and angiographic inclusion criteria and none of the exclusion criteria.

### ***8.2. Inclusion Criteria***

Subjects who meet all of the following criteria (see Table 8.2-1) may be given consideration for inclusion in this clinical investigation, provided no exclusion criterion (see Section 8.3) is met.

**Table 8.2-1: Inclusion Criteria**

Inclusion Criteria	
 
1. Subjects age 18 and older
 
2. Subject or the subject's legal representative is willing and able to provide consent before any study-specific test or procedure is performed, signs the consent form, and agrees to attend all required follow-up visits
 
3. Subject has documented chronic, symptomatic lower limb ischemia defined as Rutherford categories 2 - 4, and is eligible for percutaneous peripheral vascular intervention
 
4. Stenotic, restenotic or occlusive lesion(s) located in the native SFA and/or PPA, and meet all of following angiographic criteria by visual assessment:                     
 
i. Atherosclerotic lesion with diameter stenosis <math>\geq 70\%</math>
 
ii. Guidewire must cross lesion(s) within the true lumen, without a sub-intimal course by physicians performed, based on visual estimate
 
iii. Minimum vessel diameter proximal to the lesion <math>\geq 3</math> mm and <math>\leq 6</math> mm
 
iv. Lesion length of single or multiple focal stenosis or chronic total occlusion (CTO) lesion can be up to 15 cm long
 
v. Target lesion located at least 3 cm above the inferior edge of the femur
 
 
 
5. Patent infrapopliteal and popliteal artery, i.e., single distal runoff or better with at least one of three vessels patent (<math>< 50\%</math> stenosis by visual assessment) to the ankle or foot with no planned intervention
 

---------------------------	---

### **8.3. Exclusion Criteria**

Subjects who meet any one of the following criteria (Table 8.3-1) will be excluded from this clinical study.

**Table 8.3-1: Exclusion Criteria**

Exclusion Criteria	
 
1. Target lesion is located in the iliac artery or above the SFA
 
2. Target lesion stenosis <math>< 70\%</math>
 
3. Target lesion is moderately to severely angulated (<math>> 30^\circ</math>) or torturous at treatment segment
 
4. Target lesion/vessel previously treated with drug-coated balloon within 12 months prior to the index procedure
 
5. Target lesion/vessel previously treated with atherectomy, laser or other debulking devices prior to the index procedure
 

---------------------------	--

	

6. Target lesion/vessel with in-stent restenosis

7. Subjects who have undergone prior surgery or endovascular intervention of SFA/PPA in the target limb to treat atherosclerotic disease within 3 months prior to the index procedure

8. Use of laser or any other debulking devices other than Jetstream System (such as CTO devices or cutting balloon) in the target limb during the index procedure

9. History of major amputation in the target limb

10. Documented life expectancy less than 12 months due to other medical co-morbid condition(s)

11. Known hypersensitivity or contraindication to contrast dye that, in the opinion of the investigator, cannot be adequately pre-medicated

12. Known history of coagulopathy or hypercoagulable bleeding disorder

13. Known hypersensitivity/allergy to the investigational devices or protocol related therapies (e.g., nitinol, stainless steel or other stent materials, and antiplatelet, anticoagulant, thrombolytic medications)

14. Platelet count < 80,000 mm^3 or > 600,000 mm^3 or history of bleeding diathesis

15. Undergoing hemodialysis or concomitant renal failure with a serum creatinine > 2.0 mg/dL (176.8umol/L)

16. History of myocardial infarction (MI), stroke/cerebrovascular accident (CVA) or gastrointestinal bleeding within 6 months prior to the enrollment

17. Unstable angina pectoris at the time of enrollment.

18. History of severe trauma, fracture, major surgery or biopsy of a parenchymal organ within past 14 days

19. Pregnant, breast feeding, or plan to become pregnant in the next 12 months

20. Current participation in another investigational drug or device clinical study that has not completed the primary endpoint at the time of enrollment or that clinically interferes with the current study endpoints (Note: studies requiring extended follow-up for products that were investigational, but have become commercially available since then are not considered investigational studies)

21. Septicemia at the time of enrollment

22. Presence of outflow lesions in the target limb requiring intervention during the index procedure

23. Presence of other hemodynamically significant lesions in the target limb requiring intervention within 30 days of enrollment

--	--

	

24. Acute ischemia and/or acute thrombosis of the target lesion/vessel prior to the index procedure

25. Presence of aneurysm in the target vessel

26. Perforated vessel as evidenced by extravasation of contrast media prior to the enrollment

--	---

## **9. Subject Accountability**

### ***9.1. Point of Enrollment***

Subject, who has signed the IRB/IEC-approved study ICF, and has met all inclusion criteria and none of the exclusion criteria, will be considered eligible to be enrolled in the trial. Enrollment occurs at the time of advancement of the Jetstream catheter into the introducer sheath.

### ***9.2. Withdrawal***

All subjects enrolled in the clinical study (including those withdrawn from the clinical study or lost to follow-up) shall be accounted for and documented. While trial withdrawal is discouraged, subjects may choose to withdraw from the trial at any time, with or without reason and without prejudice to further treatment. Withdrawn subjects will not undergo any additional trial follow-up, nor will they be replaced. If a subject withdraws from the clinical investigation, the reason(s) shall be reported and documented. If such withdrawal is due to problems related to investigational device safety or performance, the investigator shall ask for the subject's permission to follow his/her status/condition outside of the clinical study. The Investigator may discontinue a subject from participation in the trial if the Investigator feels that the subject can no longer fully comply with the requirements of the trial or if any of the trial procedures are deemed potentially harmful to the subject. Data that have already been collected on withdrawn subjects will be retained and used for analysis but no new data will be collected after withdrawal.

### ***9.3. Enrollment Controls***

A minimum of 60 enrolled subjects are needed to adequately assess the primary endpoint at 30 days, assuming a maximum attrition of 15% for all reasons at 30 days. With additional 2 roll-in subjects per site, the overall subjects to be enrolled in the study are approximately 80 subjects. The enrollment cap for each study site is 35% of total enrolled subjects.

### ***9.4. Lost to Follow-up***

A subject will be considered lost to follow-up if he or she fails to return for four scheduled visits and is unable to be contacted by the study site staff.

The following action must be taken if a participant fails to return to the clinic for a required study visit:

- The site will attempt to contact the subject and reschedule the missed visit and counsel the subject on the importance of maintaining the assigned visit schedule and ascertain if the participant wishes to and/or should continue in the study.
- Before a subject is deemed lost to follow-up, the investigator or designee will make every effort to regain contact with the subject (where possible, 3 telephone calls and, if necessary, a certified letter to the subject's last known mailing address). These contact attempts should be documented in the participant's medical record or study site.
- Should the subject continue to be unreachable, he or she will be considered to have withdrawn from the study with a primary reason of lost to follow-up.

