5.10.2 Event Rates Presented Using Exact Days Cut-Off System

The denominator will be based on number of subjects who reach the protocol-defined lower window (i.e. adequate follow-up days) and/or subjects who experience the event. The numerator will be based on number of subjects-level events within the exact desired cut-off days. Subject-level events beyond the exact cut-off days will be counted as next cut-off days.

For the primary safety endpoints, the analysis will be performed with the exact days (i.e. events up to 30 days).

Follow-Up Cut-Off	Days for Adequate Follow-Up	Maximum Days to Event
30 Days ¹	23	30
182 Days	152	182
365 Days	335	365

¹All events with 1-month window will be collected. However for the primary safety endpoint, events up to 30 days post-procedure will be included.

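### Protocol 9.4 gives two conflicting rules for loss to follow-up, and under one of them 30-day MAE status learned at a later contact could not be collected

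*Protocol*

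**What the plan says.** Protocol 9.4 opens with a definition: a subject is lost to follow-up if he or she "fails to return for four scheduled visits and is unable to be contacted by the study site staff". Next comes a list of mandatory steps with a different trigger: "The following action must be taken if a participant fails to return to the clinic for a required study visit". The steps are to try to reschedule, then to attempt contact by telephone and, if needed, certified letter. The last step does not mention four visits. If the subject still cannot be reached, "he or she will be considered to have withdrawn from the study with a primary reason of lost to follow-up".

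Protocol 9.2 sets out what withdrawal means: "Withdrawn subjects will not undergo any additional trial follow-up, nor will they be replaced". Data already collected "will be retained and used for analysis but no new data will be collected after withdrawal". Its only provision for following someone further is a request for permission to do so outside the study, when withdrawal is due to device safety or performance.

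The follow-up time points are pre-discharge, 30 days, 6 months and 12 months (Protocol synopsis and 7.1). Adverse events are assessed at each of them (Protocol Table 10.1-1).

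For the primary safety rate, SAP 5.10.2 bases the denominator on the "number of subjects who reach the protocol-defined lower window (i.e. adequate follow-up days", set at 23 days, and/or subjects who have the event. Events count up to day 30. SAP 5.5 plans a worst-case analysis and a tipping-point analysis for missing primary outcomes.

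**The concern.** Losing contact with a subject is not the same as the subject withdrawing consent, yet the last step of 9.4 turns the first into the second. A subject who misses the 30-day visit and comes back at 6 or 12 months can still show whether death, major amputation or TLR had occurred by day 30. If the action list has already classed that subject as withdrawn, 9.2 forbids collecting the answer. The missing primary outcome would then be produced by the protocol's own wording.

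The two triggers in 9.4 also allow two sites to classify the same subject differently. This matters because the safety test tolerates very few events: SAP 3.1.5 allows 1 MAE in 50 subjects.

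**Working it through.** **1. Can the four-visit definition be met?** There are four follow-up time points, and the first is before hospital discharge. A subject seen then has 4 − 1 = 3 visits left and cannot miss four. For such a subject the lead sentence never applies, and the action list is the only part of 9.4 that can end in loss.

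**2. The two readings side by side, for a subject seen at discharge who misses only the 30-day visit and is unreachable at that time:**

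| | Lead sentence of 9.4 | Action list of 9.4 |
|---|---|---|
| Trigger | four missed visits, no contact | one missed required visit |
| Status | still in the study | considered withdrawn |
| 6- and 12-month contact | takes place, adverse events assessed | barred by 9.2 |
| 30-day MAE status | can be settled later | stays unknown |
| SAP 5.10.2 denominator, last seen before day 23, no known event | can be restored | subject drops out |

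The last row assumes that follow-up days run to the last contact. SAP 5.10.2 does not say which date ends follow-up.

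**3. The plan's own figures.** Inputs from Protocol 11.1.1.2: 50 evaluable, 15% attrition, 60 enrolled, PG 88%, one-sided alpha 2.5%.
- Enrolment: 50 / (1 − 0.15) = 58.8, so 59, against a stated 60. Then 60 × 0.85 = 51 evaluable and 9 missing.
- Test in SAP 7.3: Z = (p − 0.88) / √(0.88 × 0.12 / n). For 49/50: 0.10 / 0.0460 = 2.176, as the SAP prints.

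**4. Unresolved subjects counted as MAE.** SAP 5.5 does not spell out its worst case. I take it to mean that each of m unresolved subjects among 60 counts as an MAE, with no observed MAE. The standard error is √(0.88 × 0.12 / 60) = 0.04195.

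| m | MAE-free rate | Z | Against 1.96 |
|---|---|---|---|
| 2 | 58/60 = 0.9667 | 0.0867 / 0.04195 = 2.07 | pass |
| 3 | 57/60 = 0.9500 | 0.0700 / 0.04195 = 1.67 | fail |
| 9 | 51/60 = 0.8500 | −0.0300 / 0.04195 = −0.72 | fail |

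Moving from 3 unresolved to 2 changes the result.

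**5. Does the choice of bound matter?** The success criterion is a lower confidence bound, and SAP 7.3 prints both Wald and exact limits. At n = 60 the exact bound also allows 2 MAEs, so the switch stays between 2 and 3. The Wald bound allows 3, which moves the switch to between 3 and 4. Under each of them, one subject separates pass from fail.

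**The case against.** The strongest reply is that the lead sentence governs. The second step of the list is to be done "Before a subject is deemed lost to follow-up, the investigator or designee will make every effort to regain contact with the subject", and the last step uses the same term, so both can be read as relying on the four-visit definition. No deadline is set after a single missed visit. Section 9.2 names withdrawn subjects and those lost to follow-up as separate groups, and it mostly describes people who choose to leave. On this reading, a subject who misses only day 30 remains enrolled and is assessed again later.

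That reply stands to this extent: a reader might infer that one missed visit plus no contact always ends follow-up and discards the outcome. The documents do not support that as the settled rule, because it is one of two conflicting readings. But the definition does not rescue the text, since step 1 shows it cannot be met by a subject seen before discharge.

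A reader might also infer a power gain. At the assumed 99% MAE-free rate, the Z test allows 1 MAE at n = 51 (power 90.8%) and 2 at n = 57 (98.0%). Reaching 57 requires 6 of the 9 missing subjects to return, which is an assumption. With 3 returning (n = 54) power is 89.8%. Under the exact bound, n = 57 still allows only 1 MAE (88.9%). Under the Wald bound, n = 51 already allows 2 (98.5%). The 15% is moreover a maximum for all causes, not a count of unreachable subjects.

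Finally, a reader might infer that the loss is related to events. That is plausible, but nothing in the documents shows it.

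The SAP 5.5 analyses do expose dependence on missing outcomes. They do not recover them.

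**Conclusion.** The point holds as an internal contradiction in Protocol 9.4 that should be corrected. The four-visit definition cannot be met by a subject seen before discharge. The action list, followed literally, leads from one missed visit to withdrawal and, through 9.2, to a bar on collecting 30-day MAE status that a scheduled later visit could supply.

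The size is modest but can be decisive: in a missing-as-MAE check on 60 subjects with no observed MAE, one recovered subject can turn a fail into a pass. This rests on the Z test of SAP 7.3 and on my reading of the worst case. How many subjects would be affected, and how many would return, cannot be derived from the documents.

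**What to change.** - **Protocol 9.4:** replace both the four-visit sentence and the last bullet with one rule. An unreachable subject is recorded as having missed the visit, stays in the study and is contacted at each remaining visit. Loss to follow-up is assigned only when the 12-month window has closed. Subjects in whom the device is not used are followed only to 30 days (Protocol 7.1), so they need matching wording.
- **Protocol 9.2:** state that the bar on follow-up and new data does not apply to subjects who are only out of contact.
- **Protocol and SAP 5.10:** state that MAE status learned at any later contact is used, with its actual event date.

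Changing the last bullet alone would leave the four-visit definition in conflict with the new rule. The cost is a short amendment and a few extra contact attempts at visits already scheduled.

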#### **9.5. *End-of-Study Definition***

A subject is considered to have completed the study if he or she has completed all phase of the study including the last visit or the last scheduled procedure shown in the Data Collection Schedule.

The end of the study is defined as completion of the last visit or procedure shown in the Data Collection Schedule in the trial globally.

### **10. Study Methods**

#### **10.1. *Data Collection***

The data collection schedule is shown in Table 10.1-1. Please note that the time window for 30-day follow-up is +/- 7 days, for 6 or 12 months follow-up is +/- 30 days.

The table below is an overview of all the procedures or tests required per protocol. If an examination/test is required, it is marked with "X"; if it is optional but recommended, it is marked with "O".

Table 10.1-1: Data Collection Schedule

Procedure/Assessment	Screening (≤ 30 days prior to index procedure)	Enrollment	Index Procedure	Post- procedure/ Pre-hospital Discharge	Follow-up Visit g		
					30-day (± 7 Days)	6-month (± 30 Days)	12-month (± 30 Days)
In-person Visit	X	X	X	X	X	X	X
Informed Consent process, including informed consent signature date	X						
Demographics (including date of birth, gender, and race and ethnicity)	X						
Physical Assessment	X						
Medical History (including, concomitant diseases, concomitant medication and medical treatments)	X	X d	X d	X d	X d	X d	X d
Routine Laboratory (including serum creatinine, CBC with platelet count tests, and pregnancy test within 7 days of index procedure for potential child-bearing women)a	X						
DUSb	O			O		X	X
ABI	X				X	X	X
Rutherford Categories Assessment	X c				X	X	X
Angiographic assessmentb		X e	X f				
Procedural assessment (including PTA/stenting)			X f				
Adverse Events and Device Deficiency Assessment			X	X	X	X	X

X = required; O = optional but recommended

DUS = Duplex Ultrasound; ABI = Ankle Brachial Index; PTA = Percutaneous Transluminal Angioplasty

a: Excluded from the study if serum creatinine > 2.0mg/dL (176.8umol/L), or platelet count < 80,000/mm^3, or > 600,000 mm^3, or positive pregnancy test (pregnancy test is required within 7 days prior to index procedure for potential child-bearing women)

b: Angiographic and DUS recordings will be sent to the respective core labs for analysis. Follow-up angiograms and DUS will not be required for those subjects who underwent by-pass surgery of the target lesion during the 12-month follow-up time frame.

c: Inclusion criterion: Rutherford category 2 - 4

d: Antiplatelet medication assessments

e: Adhere to Angiographic Inclusion criteria.

f: Procedural (including complications), target lesion, atherectomy, PTA and/or stenting information are collected; angiographic data will be used to localize the target lesion

g: Follow-up dates will be calculated from the date of the index procedure. All follow-ups will be in-person clinic visits. The time window for 30-day follow-up is +/- 7 days; for 6 or 12-month follow-up is +/- 30 days.

## 10.2. *Study Candidate Screening*

Subjects who are suitable for PTA will be informed about the study and will be asked to sign the informed consent form (ICF) before participating in any screening procedure. After signing the ICF, the subject will receive a screening number and will be documented in a screening log. Each clinical investigator must keep a log of all screened subjects, including both eligible and non-eligible subjects (screening failures).

## 10.3. *Informed Consent*

Before any study specific tests or procedures are performed, subjects who meet the clinical inclusion criteria will be asked to sign the IRB/IEC-approved study ICF. Subjects must be given ample time to review ICF and have questions answered before signing ICF.

Study personnel should explain to the subject that even if the subject agrees to participate in the trial and signs the ICF, vascular angiography may demonstrate that the subject is not a suitable candidate for the clinical trial.

Refer to Section 9.1 for definition of point of enrollment.

## 10.4. *Screening (Up to 30 Days Prior to Index procedure)*

After a subject has signed the IRB/IEC-approved study ICF, the screening process may begin. The screening process will be used to determine the inclusion or exclusion of a subject in the study. This process includes the investigator's assessment of subject's medical records and diagnosis, and following pre-procedure data must be collected within 30 days prior to the index procedure (unless otherwise specified), for all subjects:

- Confirmation of clinical eligibility criteria (inclusion and exclusion criteria)
- Demographics including age, gender, and races others than Han (unless restricted by local laws)
- Physical assessment, including weight and height
  - Ankle brachial Index (ABI)
  - Rutherford category assessment
- Medical history (including concomitant diseases, concomitant medication and medical treatments)
- Routine laboratory tests
  - Serum creatinine
  - Complete blood count (CBC) with platelets
  - Pregnancy test for females of child-bearing potential with analysis per local practice (serum and/or urine) is required within **7 days** prior to the index procedure
- Current antiplatelet medication usage
- Duplex ultrasound (DUS) – optional (at the discretion of the investigator)

